The primary aim is to determine the efficacy of training with this exoskeleton and its ability to improve transfers to standing and sitting as assessed by the five times sit-to-stand test. A secondary aim will be to assess effects of the device during overground ambulation. Outcome measurements to investigate changes of knee range of motion and loading of the paretic limb will be accomplished using an instrumented goniometer; changes in limb loading will be monitored using a foot pressure mapping system; and stepping parameters will be recorded using the GaitRite carpet. An exploratory outcome of changes in energy expenditure during ambulation with and without the powered exoskeleton will be assessed from a 6-minute walking test using a portable metabolic cart. Another exploratory outcome measures of QOL will be determined using the SF-36 and

the Stroke Specific Quality of Life Scale. Additional exploratory outcomes to measure body composition, bone mineral density changes will be assessed using Dual X-ray Absorptiometry (DXA). Additional exploratory outcomes include measuring changes in cortical, corticospinal and spinal excitability in response to brain, spinal and peripheral nerve stimulation (PNS), and brain activation using electroencephalogram (EEG).

Baseline testing for both groups will be performed while ambulating without the device and prior to starting in the training program. The exoskeleton group will repeat testing within the first 3 sessions of the training program. Mid-point assessments will be obtained after 12 and 24 sessions of training. Post assessments will be obtained after 36 sessions of training. Retention will be assessed by repeating the assessments without the exoskeleton after 1 month of stopping the training program.

It is anticipated that longitudinal training with the device will increase number of squats achievable, increase knee flexion during swing, increase loading of the paretic limb, and induce symmetrical stepping. No immediate effect on energy expenditure by the device is expected however, a training effect is expected to demonstrate improvement in the energy cost of ambulation. Any gains observed during this study may not be retained, but as this device has the potential to be used in the home and community environment, justifying a prescription of this device for retention purposes may be warranted. Use of this device may also lead to improvement of QOL.

2. Specific Aims

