The 5xSTS is used to determine leg power and an aspect of transfer skill. This test will be used to assess a level of improved function while wearing the device. It will also be used to determine if any training effect is observed after 3 months (36 sessions) of training when not wearing the device.

Secondary Aim: To determine the efficacy of ambulation training using a powered orthotic exoskeleton on knee ROM and loading of the paretic LE while ambulating over ground with and without the device for 3 months (36 sessions).

Multiple outcome measures will be used to determine the effect of the powered exoskeleton on a person's gait biomechanics and functional competency. An instrumented goniometer will record knee joint angles during multiple gait cycles to assess changes in knee flexion during the swing phase. Because the powered orthotic exoskeleton provides stability during the stance phase, stepping parameters will be assessed using an instrumented carpet to determine if the paretic limb has more equitable and symmetrical load.

Secondary Aim: To determine the energy expenditure of ambulation with and without the powered orthotic exoskeleton at baseline and 3 months (36 sessions) post training.

A portable metabolic cart will assess oxygen consumption during the two ambulation conditions (i.e., with and without the device) over a 6-minute period. It is anticipated that the baseline comparison test will not show any metabolic changes due to the added weight of the device and negate any metabolic benefit from the motors powering the knee joint movement. However, a training effect over the 3 months (36 sessions) compared to baseline is anticipated due to the participant becoming more comfortable with the device, thus using the paretic LE more effectively.

Exploratory Aim: To determine the retained function (squatting, knee ROM, paretic LE loading and energy expenditure) 1-month post cessation of training without the device.

It is not known whether any benefits from training will be retained, but if benefits exist while wearing the device, but are not retained, then long term use may be indicated.

Exploratory Aim: To determine differences in QOL measurements (SF36 and Stroke Specific Quality of Life Scale [SS-QOL]) over 3 months (36 sessions).

The mobility portions of the SSQOL and SF36 will be used to determine whether changes in ambulation affect QOL in persons post stroke.

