5xSTS		d	d	x	d	x	d	x		
Gaitrite		w	w	x	w	x	w	x		
F-Scan	x		x			x		x		
Energy Expenditure		x		x		x		x		
Knee range while walking		w	w	x	w	x	w	x		
10mWT		d	d	x	d	x	d	x		
TUG		w	w	x	w	x	w	x		
6MWT		d	d	x	d	x	d	x		

Key: w=weekly; d=daily; x=once

during the entire gait cycle for each lower extremity. An electronic goniometer will be strapped to each lower extremity for independent and simultaneous measurement and recording of knee ROM.

Testing sessions to assess energy expenditure will be performed. Participants will be asked to wear a face mask attached to a portable metabolic cart (Oxycon Mobile, Vyaire Medical Inc.). Measurements of oxygen uptake (VO_2), heart rate (HR) and respiratory rate (RR) will be assessed and recorded. These measurements will be acquired during 6 minutes of quiet sitting (rest) followed by ambulating at a comfortable, self-selected pace for 6 minutes.

The Fugl-Meyer Assessment Lower Extremity (FMA-LE) will be used as a general score of lower extremity motor and sensory function/post-stroke recovery (34). General changes in QOL will be assessed using the SF36 (35) and SSQOL scales (36).

A Dual X-Ray Absorptiometry (DXA) will be used to determine changes in body composition and bone density. A scan of the total body will be used to view changes in bone mineral content (BMC), lean mass, and fat mass. Scans of both hips, and both knees will be used to compare bone mineral density (BMD).

Motor responses will be measured using surface electrodes placed on the participants skin over key muscles to determine changes in cortical, corticospinal and spinal excitability. These responses will be brought about using either transcranial magnetic stimulation (TMS), transcutaneous spinal cord stimulation (TSCS) or PNS. TMS uses electromagnetic pulses, while TSCS and PNS use a series of electrical pulses. Whether it is stimulation over the brain, spine or peripheral nerve, stimulation causes the targeted muscles to twitch. These twitches are then recorded and compared.

EEG will be used to measure changes in brain activation. A 64 electrode EEG cap will be placed on the subjects head and will record brain activity during a resting state.

Description of Data and Statistical Analyses

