The loading profile obtained from the F-Scan foot pressure system will be normalized over the gait cycle as percentage of gait cycle and percentage of body weight for each foot. The total area under the curve will be calculated to obtain a total load on each lower extremity. Peak measurements from heel strike and toe-off will be calculated from the curve along with mid stance where load is typically diminished. Maximum knee flexion angles from 10 continuous steps will be averaged for each limb.

Metabolic measurements (VO_2 , HR and RR) will be recorded as averages every minute. Energy cost of distance travelled will be calculated by dividing VO_2 normalized to body weight (ml/kg/min) by the distance traveled (ml/kg/m). The 6 values from the consecutive 1-minute recordings will be averaged for sitting and walking conditions.

Descriptive statistics will be employed for demographic and Fugl-Meyer data. A single group, repeated measures design will be employed in the experimental group to test the within-group effect of using the powered exoskeleton. A two group repeated measures design will be employed to test the between-group differences in outcomes. All outcome measurements will be analyzed using a mixed model ANOVA to determine significant main and interaction effects of group (control, experimental) and time (baseline, session 36, 1-month follow-up). A similar mixed model ANOVA will be used to determine significant main and interaction effects of the two conditions (without [w/o] and with [W] Keeogo exoskeleton) in the experimental group for the 3 time points (baseline, session 36, 1-month follow-up). Post hoc analyses of significant data will be performed using t-tests.

Table 3: Timeline of activities to complete the study

TIME LINE	Year 1				Year 2			
	Q1	Q2	Q3	Q4	Q1	Q2	Q3	Q4
Start-up Activities								
IRB & R&D	x				x			x
Staff Hiring and Training	x							
Purchase Equipment	x							
Database development	x							
Participant Screening	x	x	x	x	x	x		
Participant Enrollment	3	4	4	3	1	0		
Database management	x	x	x	x	x	x		
Abstract writing				x	x	x		
Manuscript writing					x	x		

Potential Difficulties and Limitations

The greatest hurdle in conducting investigations with devices is recruiting participants and completing the training as well as obtaining regulatory approval to conduct the study. Feasibility to enroll and complete the 15 participants is

Protocol ASS-20-01

MIRB# 01929

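### Walking oxygen uptake is averaged over all six minutes, so it includes the rise from seated rest and understates steady-state energy cost; the effect on change depends on kinetics the plan does not measure

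*Combined protocol and SAP*

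**What the plan says.** Research Design and Methods (Outcome Measurements and Testing sessions) sets the order of the test: "These measurements will be acquired during 6 minutes of quiet sitting (rest) followed by ambulating at a comfortable, self-selected pace for 6 minutes". No standing phase, warm-up or unrecorded lead-in is described.

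Description of Data and Statistical Analyses says that VO2, heart rate and respiratory rate "will be recorded as averages every minute". It defines energy cost as weight-normalised VO2 over distance, in ml/kg/m, and then states: "The 6 values from the consecutive 1-minute recordings will be averaged for sitting and walking conditions". No minute is dropped and no steady-state window is named. That this average feeds the energy-cost formula is implied by the adjoining sentences; no other walking VO2 is defined.

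The outcome's standing varies. Specific Aims lists it as a secondary aim: "To determine the energy expenditure of ambulation with and without the powered orthotic exoskeleton at baseline and 3 months (36 sessions) post training". The opening summary calls it "An exploratory outcome of changes in energy expenditure during ambulation with and without the powered exoskeleton". Both places expect a gain. The summary says "a training effect is expected to demonstrate improvement in the energy cost of ambulation", and Specific Aims says "a training effect over the 3 months (36 sessions) compared to baseline is anticipated". Neither gives a size.

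**The concern.** VO2 does not reach its walking level at the first step. A mean taken from the start of the walk therefore mixes two quantities: the cost of walking, which is what the aim concerns, and the speed at which uptake rises from rest. The bias in the level of VO2 is downward.

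Two things are at stake. First, the reported walking VO2, and energy cost at a given speed, will be too low as steady-state values. Specific Aims intends the results to help power later studies, so these figures may be carried forward. Second, if the speed of the rise differs between baseline and session 36, or between walking with and without the device, part of the observed difference will reflect kinetics and not cost.

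**Working it through.** The plan states no expected value, effect size or variance for energy cost, so there is no figure of its own to reproduce.

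**Inputs from the protocol.** Six one-minute values, none dropped. Rest R = 3.5 and walking S = 11.2 ml/kg/min come from Preliminary Studies (eight participants with spinal cord injury, another exoskeleton) and serve as illustration only.

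**Assumptions, not in the protocol.** A mono-exponential rise; a time constant τ of 30-60 s (20-90 s for range); a true reduction of 10% in steady-state VO2.

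**Formula.** With uptake S − (S − R)·exp(−t/τ), the mean from minute a to minute b is S − (S − R)·k, where k = τ·[exp(−a/τ) − exp(−b/τ)]/(b − a) and τ is in minutes. The share of the rise captured is 1 − k. Percentages below use unrounded values.

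**Step 1: share of the rise captured.**

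| τ | k, minutes 1-6 | captured | k, minutes 4-6 | captured |
|---|---|---|---|---|
| 30 s | (0.5/6)(1 − e^−12) = 0.083 | 91.7% | 0.0004 | 99.96% |
| 45 s | (0.75/6)(1 − e^−8) = 0.125 | 87.5% | 0.0045 | 99.6% |
| 60 s | (1/6)(1 − e^−6) = 0.166 | 83.4% | 0.0158 | 98.4% |

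**Step 2: level.** S − R = 7.7. At 30 s the six-minute mean is 11.2 − 7.7 × 0.083 = 10.56, which is 5.7% low. At 60 s it is 11.2 − 7.7 × 0.166 = 9.92, which is 11.4% low. Minutes 4-6 are 0.0% and 1.1% low. Over τ = 20-90 s the six-minute understatement runs from 3.8% to 16.9%; at 90 s minutes 4-6 are still 4.0% low. If 11.2 is itself a six-minute mean, the 30-60 s range becomes 5.9% to 12.1%. With a steady state of 7 ml/kg/min it is 4.2% to 8.3%.

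**Step 3: change, kinetics unchanged.** A true 10% fall takes S to 10.08, a drop of 1.12.
- 30 s: 10.56 to 9.53, a drop of 1.03. This is 92% of the absolute drop, read as 9.7%.
- 60 s: 9.92 to 8.99, a drop of 0.93. This is 83% of the absolute drop, read as 9.4%.

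**Step 4: gain from walking farther only.** Let speed go from 0.45 to 0.50 m/s (27 to 30 m/min) with VO2 mean M and τ unchanged. Cost goes from M/27 to M/30, a fall of 1 − 27/30 = 10% whatever M is. Nothing is lost.

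**Step 5: change, kinetics differ; true reduction 10%.**

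| τ before → after | minutes 1-6 | reads | minutes 4-6 read |
|---|---|---|---|
| 60 → 45 s | 9.92 → 9.26 | 6.7% | 9.3% |
| 60 → 30 s | 9.92 → 9.53 | 3.9% | 9.0% |
| 45 → 60 s | 10.24 → 8.99 | 12.2% | 10.7% |

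The last row reverses the first: 10.08 − 6.58 × 0.166 = 8.99, and (10.24 − 8.99)/10.24 = 12.2%. For minutes 4-6, (11.17 − 9.98)/11.17 = 10.7%.

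**The case against.** The strongest reply is that the same rule applies to every arm, visit and device condition, so a level error largely cancels in relative change. Step 3 bears this out, and Step 4 shows that a gain from distance alone is untouched. Both arms also train for 36 sessions at the same target exertion, so a training effect on kinetics common to both would cancel, to that extent, in the group-by-time interaction. This stands. It does not protect the with- versus without-device contrast if kinetics differ between those conditions.

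A second reply is that any masking would be conservative. That holds only if the rise becomes faster; a slower rise exaggerates the reduction (last row of Step 5).

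Third, most of the distortion lies in the first minute: under the same model minute 2 already captures 94% (30 s) or 77% (60 s) of the rise, and minute 3 captures 99% or 91%. This is correct. It would be wrong to say that the first three minutes tell us nothing about cost.

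Fourth, six-minute VO2 over six-minute distance is matched in time, whereas late VO2 over whole-walk speed would be mismatched for anyone who changes pace. This also stands, and the fix below matches the two. Finally, the rule is consistent with the team's earlier work, where data were averaged within each six-minute phase. That explains the choice but does not remove the transient.

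**Conclusion.** The plan as written understates steady-state walking VO2, and energy cost at a given speed, by about 6% to 11% under the stated assumptions. Absolute VO2 differences shrink to 83% to 92% of their true size. The direction of the level bias follows from the averaging rule and the test sequence. The size rests on an assumed exponential rise with a time constant of 30-60 s, and on rest and walking values from a different population and device.

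A reader might infer that the rule will hide the training gain that the trial expects. The documents do not support that. With unchanged kinetics a true 10% reduction still reads 9.4% to 9.7%. Appreciable masking needs a faster rise after training, on which the protocol gives no data. What can be said is that the six-minute mean leaves the comparison open to such a shift, and minutes 4-6 much less so.

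Severity is minor. The outcome is secondary in Specific Aims and exploratory in the summary, and the primary outcome, the sit-to-stand test, is unaffected.

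**What to change.** In Description of Data and Statistical Analyses, define walking VO2 for the energy-cost outcome as the mean of minutes 4-6, divided by walking speed over those same minutes. Record distance at the end of minute 3 as well as at minute 6; speed in m/min is then the difference divided by 3, which yields the ml/kg/m the plan names. Use the same window in both arms, both device conditions and all visits. Report the six-minute mean as a sensitivity analysis. The sitting-rest rule can stay: the energy-cost formula does not subtract rest.

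The cost is a sentence or two of text and one extra distance reading per walk, since the one-minute VO2 values are already planned. Three values are averaged in place of six. A participant who stops before completing minute 4 has no late-window value; only the value under the six-minute rule is available, and it should be reported separately. With 12 completers expected, the number of such cases should be stated.

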[figure not shown]

Figure 2: Box plot of oxygen uptake (VO₂) is displayed for each condition (SIT, STAND and WALK) and estimated maximal (Max) predicted VO₂ using predicted equations from leg and arm crank exercises. Significant differences ($p < 0.001$) were found between WALK compared with SIT and STAND (2).

[figure not shown]

Figure 3: Box plot of heart rate (HR) is displayed for each condition (SIT, STAND and WALK) and estimated maximal (Max) predicted HR. Significant differences ($p < 0.001$) were found between WALK compared with SIT and STAND. BPM = beats per minute (2).

benefit leading to increased use of the paretic limb even while not wearing the exoskeleton. With long-term use of this device, potentially this device could be used to combat muscle and bone loss in the paretic limb.

Research Design and Methods

Participants, Eligibility and Recruitment

Strategies: Fifteen persons with stable, chronic stroke (>6 months) will be recruited through the various outpatient clinics that treat Veterans with stroke at the James J Peters VA Medical Center (JJPVAMC). There were approximately 402 unique Veterans with chronic stroke who obtained services during 2018 at the JJPVAMC.

This would provide ample potential participants to prescreen 50 Veterans, as outlined in Table 1. It is expected that a portion (n~40) will express interest in signing informed consent, after which further screening will be performed. Candidacy will be determined based on the following inclusion and exclusion criteria: age between 18 and 89; weight under 250lbs, medically stable; and able to stand and initiate steps on their own with walking speed between 0.15-0.75m/s, but with chronic gait impairments such as reduced knee flexion and reduced time spent on the paretic limb during stance phase. A detailed list of the inclusion and exclusion criteria are presented in the Human Subject's section of this application. Because the effects of paralysis from stroke are believed to overpower the effects of age, gender or ethnicity, these demographic characteristics will not be restricted. A total of 15 participants are expected to enroll in the trial, however, to account for attrition, it is expected that 12 participants will complete the trial within the 2-year period.

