Randomization: Eligible participants will be randomized into either the exoskeleton group or control group. Block randomization will be used with a 2 to 1 ratio to result in 10 participants in the exoskeleton group and 5 participants in the control group (30). This ratio was chosen because future proposals will be focused on home and community use of the device, therefore more pilot data showing safety and feasibility is needed.

Description of Training Sessions: All participants will visit the JJPVAMC for 36 training sessions, 3 times per week for 3 months and will follow the recommendations of the American Heart Association (AHA) and American Stroke Association (ASA) (20). Those in the exoskeleton group will train using the Keeogo powered exoskeleton and those in the control group will train without the exoskeleton using their conventional assistive devices. Training sessions will be progressive, with duration to tolerance for a minimum of 20 minutes and a maximum of one hour. Training will consist of mobility activities affecting daily life including: walking; squatting (or getting in and out of a chair); bending, kneeling or stooping (for picking an item up off of the floor); and ascending and descending stairs. Sessions will be monitored and tailored to the individual, based on their functional ability and to ensure their safety. Exertion will be maintained at a level between 11-14/20 using the Borg scale (31), as per recommended by the AHA and ASA (20). All participants will be allowed to take as many breaks as needed during each session.

Technical Description of the Keeogo™ Powered Orthotic Exoskeleton: Those randomized into the powered exoskeleton group will be using the Keeogo™ (B-Temia Inc., Quebec City, QC, Canada) (32), which is a powered orthotic exoskeleton, designed for users who have difficulty ambulating and/or need assistance with movement of the knee (Figure 4). This device does not restrict movement and only provides assistance at the knee during extension and flexion during ambulation, standing up, sitting down and when ascending or descending stairs. It is not intended for use in those who have complete paralysis of their leg as it requires some active movement to assist with. The Keeogo™ weighs Protocol ASS-20-01
MIRB# 01929

Table 1: Recruitment efforts

	Year 1				Year 2				Totals
	Q1	Q2	Q3	Q4	Q1	Q2	Q3	Q4	
Pre-Screening	10	10	10	10	10	0	0	-	50
Screening	-	7	10	10	10	3	0	-	40
Enrollment	-	3	4	4	3	1	0	-	15

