This device separates itself from the other powered exoskeleton devices (e.g., Indego, Ekso) because it only provides assistance to the knee joint and requires the user to have some ability to ambulate independent of the device. Therefore, the user must be able to initiate the active movement, which will then be enhanced by assistance from the Keeogo. The system assists the knee to enhance user-initiated movements by using kinetic and kinematic data from sensors located at the knee and hip joints to assist in all phases of the gait cycle, i.e. knee flexion and extension in swing phase, knee extension (both eccentric control and concentric assist) in stance phase. In addition to gait, the device assists during other functional lower extremity activities, i.e. squatting motions, kneeling, walking, stair climbing and stand-sit/sit-stand transfers. Keeogo™ has two essential functions: (1) to provide kinematic amplification during the swing phase of gait and (2) to provide stability for the stance phase of gait through knee bracing coupled with non-linear spring-like assistance. Keeogo™ is designed to operate intuitively through automatic sensing and augmenting the user's natural walking movement. The eccentric control assists during the gait cycle at initial contact (loading response), squat (Figure 5), kneel, stand to sit and stairs. The eccentric control applies the torque gradually, thus stabilizing the knee and preventing buckling.

Figure 5: Squatting in the Keeogo

Outcome Measurements and Testing sessions: The timeline for conducting testing sessions is outlined in Table 2. Screening participants and obtaining their medical history and demographics will be obtained once, prior to initiating training. Baseline assessments that do not involve the exoskeleton will be obtained prior to training in both groups. Baseline assessments, which involve the exoskeleton (for the exoskeleton group only) will be obtained during the first three sessions after the participant has been correctly fitted and acclimated to the exoskeleton. Testing will be repeated after training session 36 (3 months) without the exoskeleton for both groups and repeated with the exoskeleton for the exoskeleton group. All participants (control and experimental) will be asked to return 1-month post cessation of training for a follow-up visit where all the outcome measures will be repeated without the exoskeleton for both groups (Table 2) to assess retention of functional gains.

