The 5xSTS test will be used to address the primary aim of improving participants' squatting ability (LE Strength) (33). This test is performed using a standard free-standing chair with a straight back, solid seat and a seat height of 17 inches. Participants will be instructed with the following statement "By the count of 3, please stand up and sit down as quickly as possible for 5 times. Place your hands on your lap and do not use them throughout the procedure. Lean your back against the chair's backrest at the end of every repetition." The time to complete the test will be recorded and will start once the person back leaves the back rest and stops once the back touches the back rest for the 5th time.

Assessment of gait changes will be performed using the GaitRite Carpet (CIR Systems Inc), the F-scan foot pressure system (Tekscan) and the instrumented goniometer (bendlabs). These measurements will be performed with and without the device. The GaitRite measurement will be obtained by asking each participant to walk over a carpet equipped with sensors, which provide information regarding cadence, step length and time spent on each foot. The F-Scan foot pressure system requires the participant to walk with a disposable insole, which is cut to fit inside their shoe. The disposable insole contains an array of sensors, which provide a continuous pressure profile of each foot during ambulation. This system will measure the percentage of total body weight loaded during the different segments of the stance phase (heel-strike, stance and toe-off) as well as Protocol ASS-20-01

MIRB# 01929

Table 2: Timeline for testing and training

Week:	Schedule of Procedures and Testing									
	-2 to -1	-1	1-4	4-5	5-8	8-9	9-12	12-13	16	
Phase	Pre Screen	Screening /Baseline Testing	Training	Assessments	Training	Assessments	Training	Post Assessments	1-Month Follow-up	
Chart reviews	x									
Consent	x									
Medical History/ Demographics		x								
Fugl-Meyer		x		x		x		x		x
EEG	x		x					x		x
Neuronal Excitability		x						x		x
DXA	x							x		
QOL(SF36 and SSQOL)		x						x		
Training session number			1-3	3-12		12-24		24-36		
Assessments with out Keeogo (both Control and Exoskeleton group)										
5xSTS	x	d	d	x	d	x	d	x		x
Gaitrite	x	w	w	x	w	x	w	x		x
F-Scan	x			x		x		x		x
Energy Expenditure	x			x		x		x		x
Knee range while walking	x	w	w	x	w	x	w	x		x
10mWT	x	d	d	x	d	x	d	x		x
TUG	x	w	w	x	w	x	w	x		x
6MWT	x	d	d	x	d	x	d	x		x
Assessments with Keeogo (only Exoskeleton Group)										

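### The between-arm analysis of 10 versus 5 participants has no regression adjustment for baseline 5xSTS, so a chance baseline gap, which is likely to be sizeable, passes partly into the estimate

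*Combined protocol and SAP*

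**What the plan says.** The section on data and statistical analyses states "A two group repeated measures design will be employed to test the between-group differences in outcomes". The model is a "mixed model ANOVA to determine significant main and interaction effects of group (control, experimental) and time (baseline, session 36, 1-month follow-up"). Baseline is therefore part of the outcome vector, and no baseline covariate is named. The section does not say which term is the treatment effect. It adds that "Post hoc analyses of significant data will be performed using t-tests", without saying whether these use raw values at a visit or changes.

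Under Randomization: "Block randomization will be used with a 2 to 1 ratio to result in 10 participants in the exoskeleton group". The remaining 5 of the 15 are controls. No stratification or minimisation is described.

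Under Outcome Measurements: "Baseline assessments that do not involve the exoskeleton will be obtained prior to training in both groups", and "The 5xSTS test will be used to address the primary aim". A without-device baseline is thus planned for every participant. On attrition, the recruitment text says "it is expected that 12 participants will complete the trial within the 2-year period".

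**The concern.** With five controls, the arms can easily start at different levels of 5xSTS. Eligibility allows ages 18 to 89 and a fivefold range of walking speed (0.15 to 0.75 m/s), so starting values are likely to vary widely.

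Subtracting baseline removes a gap fully only if baseline and follow-up are perfectly correlated. Otherwise the arm that starts slower tends to improve more through regression to the mean, and this appears as a treatment effect in its favour. The group main effect has a different fault: it averages a visit that precedes treatment into the comparison.

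The Specific Aims say that these results should help to size later studies. An estimate shifted by a chance gap, or diluted by the baseline visit, would carry over into that sizing.

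**Working it through.** **Inputs from the documents.** Arms of 10 and 5; three time levels (baseline, session 36, 1 month); 12 expected completers. No alpha, power, effect size, SD or correlation is stated, so there is no figure of the plan's own to reproduce.

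**Assumptions.** SD of 5xSTS = 1 at every visit; the same correlation r between any two visits, from 0.3 to 0.9; a linear relation with a common slope in both arms; completers split 8 versus 4.

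**1. Size of a chance baseline gap.** SE = sqrt(1/10 + 1/5) = 0.55 SD. P(|gap| > 0.5 SD) = 2 × [1 − Φ(0.5/0.548)] = 36%. With 8 versus 4, SE = sqrt(1/8 + 1/4) = 0.61 SD and the probability is 41%.

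**2. What a gap does to each estimate.** For a baseline gap g (exoskeleton minus control):
- Change from baseline to session 36 (the interaction contrast): expected shift (r − 1) × g. For g = 0.5 SD the size is 0.5 × 0.5 = 0.25 SD at r = 0.5, 0.3 × 0.5 = 0.15 SD at r = 0.7, and 0.1 × 0.5 = 0.05 SD at r = 0.9.
- Group main effect over three visits: a constant effect of 1 is recovered as (0 + 1 + 1)/3 = 0.67. The share of the gap carried is (1 + 2r)/3, which is 0.67 at r = 0.5, 0.80 at 0.7 and 0.93 at 0.9.
- t-test on raw session-36 values, if that is what is meant: shift r × g.
- Baseline as covariate: shift 0.

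Simulation (40,000 trials per setting, true effect 1 SD) agrees. The change contrast averaged 1.00 at every r, with slopes on the gap of −0.50, −0.30 and −0.10 at r = 0.5, 0.7 and 0.9. The main effect averaged 0.67. The covariate model had a slope of about 0.

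**3. Precision.** In units of (1/n1 + 1/n2), the variance of the change contrast is 2(1 − r). With baseline as covariate it is (1 − r²) × (N − 3)/(N − 4), where the last factor is the cost of estimating the slope. The ratio is (1 + r)/2 × (N − 3)/(N − 4).

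| r | 10 vs 5 (factor 12/11) | 8 vs 4 (factor 9/8) |
|---|---|---|
| 0.5 | 0.82 | 0.84 |
| 0.7 | 0.93 | 0.96 |
| 0.8 | 0.98 | 1.01 |
| 0.9 | 1.04 | 1.07 |

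Setting the ratio to 1 gives break-even at r = 2 × 11/12 − 1 = 0.83 for N = 15, and 2 × 8/9 − 1 = 0.78 for N = 12.

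**The case against.** The strongest reply is that the planned interaction already uses baseline. Each person's baseline is subtracted, and over all randomisations the contrast is unbiased. This stands. A reader might infer that the analysis ignores baseline or is biased outright; the documents support neither. What is missing is regression adjustment, and the shift is conditional on the gap that this one trial happens to draw.

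A reader might also infer that the plan necessarily loses precision. That depends on r, which the documents do not give. The gain from adjustment is material near r = 0.5, small at 0.7 and reversed at 0.9. With 12 completers it is gone by r = 0.8.

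A third tempting reading is that unequal arm sizes make the p-values unreliable through pooled variances. The documents do not support it as a finding: they specify no residual variance structure and give no evidence that the arm SDs differ. Allowing arm-specific variances also has a price. For a 1 SD effect at r = 0.5 with equal variances, a t-test on change in 10 versus 5 has about 40% power when pooled and about 37% with the Welch form.

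Finally, this is a pilot, and part of the primary aim is a with-versus-without-device comparison inside the exoskeleton arm, which between-arm adjustment does not touch. That is true, and it limits the weight of the point. The plan nevertheless chooses to test the arms against each other, and the data for a better estimate are scheduled for everyone.

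**Conclusion.** The point holds as one about conditional robustness and an unnamed estimate. A baseline gap above 0.5 SD has a 36% chance at 10 versus 5 (41% at 8 versus 4). At a gap of exactly 0.5 SD the change contrast is off by 0.25 SD (r = 0.5) or 0.15 SD (r = 0.7). The group main effect is the weakest of the planned terms, because it is diluted to about two thirds and most exposed to the gap.

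The probabilities rest on normal sampling and, for completers, on the 8 versus 4 split; the shifts rest on assumed values of r. Adjustment does not make the comparison confirmatory. At 10 versus 5, taking two-sided 5% and 80% power as assumptions, the detectable effect moves only from 1.66 to 1.51 SD at r = 0.5 and from 1.29 to 1.25 SD at r = 0.7. This is a worthwhile improvement to the plan, not a defect that invalidates it.

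**What to change.** State that the between-arm estimate is the difference in 5xSTS without the device at session 36, with the 1-month difference handled likewise. Obtain it from a model with baseline 5xSTS as covariate, or from a repeated-measures model that constrains the arms to a common baseline mean, and report it with a confidence interval. Do not use the group main effect as the treatment effect. Use the same approach for other continuous outcomes that have a baseline. Arm-specific variances should be at most a sensitivity analysis.

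The cost is a change of wording and one degree of freedom. If r is as high as 0.9, variance rises by about 4% at 10 versus 5, or about 7% at 8 versus 4. In return, the estimate no longer depends on the baseline gap that chance produces, under the linear common-slope assumption.
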